3.5 Cost-effectiveness analysis

Even if clinical strategies, such as universally offered screening for STIs, are proven to be effective, the costs of those strategies compared with usual care or more targeted approaches may make them impractical and unsustainable in a cost-constrained healthcare system. Cost-effectiveness analysis is a commonly used tool that allows policy makers and clinicians to measure the benefits gained for the additional costs of such strategies. The result of a cost-effectiveness analysis is the incremental cost-effectiveness ratio (ICER), which describes the additional cost of the more expensive but more effective strategy being examined, in this case universally offered STI screening, compared with the lesser cost of the less effective strategy (we have hypothesized this will be targeted screening) divided by the measure of effectiveness being considered. The most commonly used metrics in the peer-reviewed medical literature examine the incremental cost per quality-adjusted life year (QALY) gained; however, any meaningful measure of effectiveness can be used. For this project, we plan to look at additional cost per STI detected, as well as cost per QALY gained. We will develop decision analytic models (using Markov state transition structure) to evaluate the cost-effectiveness of universally offered screening compared

with targeted screening. To be complete, we also will include usual care as a third strategy. A simple model will only examine effectiveness in terms of STIs detected. A more complicated model will include short- and long-term consequences of treated and untreated disease. Short-term outcomes will include the likelihood of follow-up and treatment once a diagnosis has been made, along with the efficacy of antibiotic therapy. Based on test characteristics from the literature, small numbers of patients may have false positive or false negative test results. We will model the consequences of both, in terms of additional costs and consequences of unnecessary treatment for false positives, and the costs and consequences of undetected/untreated STI in the case of false negatives. Outcomes also will be modeled for unscreened patients who later return for treatment of symptomatic disease (e.g., acute pelvic inflammatory disease). Long-term outcomes addressing the sequelae of untreated/ undetected STIs (tubal infertility, ectopic pregnancy, and chronic pelvic pain) and outcomes following successful detection and treatment will be modeled. Data generated from Aim 2 regarding the effectiveness of the two screening strategies in detecting GC/CT, the proportion of identified patients who ultimately receive treatment, and the prevalence ranges of GC and CT in cohorts presenting for ED care at the 6 sites in our study, will be used to inform probabilities in the model. Literature-based estimates will inform other probabilistic events and costs of long-term STI sequelae in the model. Incremental cost-effectiveness ratios will be calculated to determine cost-effectiveness. The analysis will use a health care sector perspective³⁴ that includes medical costs borne by third-party payers and paid out-of-pocket by patients. These will include current and future costs related to both the intervention and downstream events related to treated or missed STIs. We will perform a series of deterministic sensitivity analyses to explore the impact of parameter uncertainty on results, and known population variations. A key parameter of interest is the background rate of STI. This likely varies from location-to-location, and will be a key determinant to the cost-effectiveness of the universally offered screening strategy. We will calculate the threshold of background STI prevalence above which universally offered screening becomes very cost-effective (i.e., an ICER <\$50,000/QALY). As a result, the cost-effectiveness of the universally offered screening strategy may vary from location to location in the study, and in real-world use of the screening tool. Understanding this threshold may help shape policy for optimal screening strategies in different locations and settings.

4 Study Procedures

Human Factors Workflow Analyses: Human factors workflow evaluations will occur at each of the 6 participating sites. A convenience sample will be obtained during the times of CRC availability. These observations will be conducted to understand

[figure not shown]

Figure 3: Study Design.

site-specific ED flow differences that may occur with respect to the care of adolescents. We will collect observational data regarding ED workflow and information exchange using the tool TaskTracker³⁵ to record clinical workflow and identify common workflow paths.

Pragmatic Trial: Once the ideal workflow strategy is identified at each individual site, all participants in both the targeted and universally offered screening phases will use a handheld tablet device to provide electronic informed consent for participation. All participants will complete the previously developed and validated ACASI SHS containing questions regarding their personal sexual health history.³⁶ The PROs tool will risk-stratify patients for STIs based on their reported sexual experience and/or presence of STI-related symptoms. Using the tablet device, patients will also indicate their interest for clinician-ordered STI testing (urine-based GC/CT). This will provide clinicians real-time EHR-integrated decision support for GC/CT testing.

4.1 Screening and Enrollment

Since this is a pragmatic trial, the exact process of distributing tablets may differ by site and will be further clarified during the workflow analyses. At some sites registration staff may be responsible for tablet distribution and at other sites triage or bedside nurses may distribute the tablets. This will depend on the results of the workflow analysis. The electronic informed consent document will contain information about the study. Should questions arise, RCs will be available to answer more detailed questions. Research staff are available at each participating ED up to 16 hours per weekday and between 8-16

Patient Classification	CDS
At High Risk	STI Testing Highly Recommended
At Risk	STI Testing is Recommended
At Low Risk	STI Testing Not Necessary at this time

Table 1: STI Testing CDS

hours on weekends. During hours without RC presence, there will be a research-trained clinical provider (with both protection of human subjects and good clinical practices (GCP) training) present to answer questions. Reasons for not offering the tablet will be recorded by the ED staff. Furthermore, if adolescents decline study participation, a reason for refusal will also be recorded on the tablet.

- **Targeted screening:** During the targeted screening intervention, data from the SHS will be integrated into the EHR and will provide CDS for GC/CT testing based on SHS-calculated STI risk (developed and validated by [name]). Patients will be classified as at high risk for STIs if they disclose being sexually active and have either the presence of STI-related symptoms or any of the following high risk behaviors: more than 1 sexual partner in the last 3 months, no condom use during last sex or prior history of STI. Patients will be classified as at risk if they disclose being sexually active but do not disclose having any STI-related symptoms or any high-risk sexual behaviors. Patients will be classified as at low risk if they deny any history of sexual activity (see preliminary data for STI positivity rates by risk strata). When patients classify as at high risk, clinicians will receive CDS that STI testing is highly recommended; when they care for patients who classify as at risk, they will receive CDS that STI testing is recommended; when caring for patients who classify as at low risk, they will receive CDS that STI testing is not necessary at this time. If the clinician chooses to follow the recommendation for screening based on patients risk assessment, and the patient consents to testing on the tablet device, urine GC/CT testing will be performed.
- **Universally offered screening:** During the universally offered screening intervention, STI screening will be offered to all eligible adolescents, regardless of risk. All eligible patients will also complete the SHS, will be informed of the CDC GC/CT testing recommendations and then be given the option to decline STI testing using the tablet device. During this phase, the SHS results will not be available to the clinician. STI testing recommendations will be based only on the patients decision to undergo GC/CT testing. Like the process followed in the targeted screening phase, if the clinician follows the CDS that informs the clinician that the patient

agreed to GC/CT screening and consequently orders testing, urine GC/CT testing will be performed.

- **Both approaches:** If the patient is at risk for STIs and declines GC/CT testing, or the patient simply declines GC/CT testing on the tablet but the clinician believes the patient should be tested, the clinician will have the opportunity to engage in a shared decision-making process with the patient as per routine clinical care. Alternatively, if the clinician declines the CDS GC/CT testing recommendations, he/she will be asked to electronically document the reason the CDS is not being followed. All patients who test positive for an STI will be notified of their results and provided treatment based on each sites standard clinical processes for result notification and treatment. Among all patients tested for GC/CT, the associated primary care clinician (PCP) will be informed of the testing and results via existing communication methodologies including Epic in-basket messages, faxes, or other electronic communication methods, and both patients and clinicians will be encouraged to schedule outpatient follow-up appointments. Medical staff, including faculty, clinical trainees, nurses and other medical support staff, will be educated about each screening intervention prior to implementation and with frequent reminders, through in person staff meetings, emails, and Epic job aids.

4.2 Surveys

All data entered into the tablet by either the ED personnel or the patient will be stored at the study site. This information will include the patients medical record number, encounter ID, patients electronic consent to participate in the study, and survey responses. For those patients who either do not meet inclusion criteria or refuse participation, exclusion/refusal reasons will be documented by the staff and/or patients electronically and stored in this database.

During implementation of the targeted screening intervention, the patient responses to the SHS survey will categorize patients as at high risk, at risk, or at low risk for STIs. This composite score will then be transmitted to the EHR through the Bridges Interconnect system, a secure native interface allowing one-way transmission of data into Epic. Bridges Interconnect is used to send data outside the Epic EHR into the EHR and is available at all participating sites. CDS will be triggered on the EHR based on STI risk strata as calculated by the SHS. During implementation of the universally offered screening, CDS for GC/CT screening will be determined by the patients decision to be screened. If a patient agrees to GC/CT screening, that information will be transmitted to the EHR through the Bridges Interconnect system, which will then trigger GC/CT

screening CDS for the clinician.

5 Data Analysis

5.1 Specific Aim Analyses

Specific Aim 1. To compare the effectiveness of usual care, targeted screening and universally-offered screening in EDs through a pragmatic trial that applies a human factors systems approach to implement GC/CT screening into routine clinical care.

Human Factors Workflow Analyses: Data will be aggregated across observations and workflow analysis will be performed to identify the most frequent tasks and interactions during an ED visit. Transition diagrams will be created to examine overall workflow processes which will include tasks performed, communication events between clinicians and patients, and interactions with technology. Common patterns of activity will be identified and used to inform deployment of the application to the patient and integration with the EHR.

Pragmatic Trial: We will report descriptive statistics to summarize each primary and secondary outcome variable. Our primary comparison of GC/CT screening strategies will be targeted vs. universally offered. We will compare detection rates (number of STIs detected divided by the number of eligible, asymptomatic patients) using site 2-week period as the unit of analysis. Standard stepped-wedge analysis techniques will be used. Specifically, the site detection rate over each 2-week period will be the outcome in a linear model to examine the effect of screening strategy on detection rate. In the model, we will include a fixed effect for each site. To control for temporal trends, we will model the effect of time as a piecewise linear function with 8 three-month segments (i.e., cutpoints at the following times on the two-week scale: 0.5, 7, 13.5, 20, 26.5, 33, 39.5, 46, and 52.5 weeks). A three-level intervention effect will be included, and we will test for a difference between targeted and universally offered screening at a 5% significance level. We will perform a similar analysis using the outcome of rate of positivity among those tested for GC/CT. We will also calculate the proportion of visits during which eligible patients agreed to GC/CT testing and compare them across the 2 STI screening strategies (targeted vs. universally offered). We will calculate the proportion of visits during which clinicians follow the GC/CT testing CDS recommendations across the 2 GC/CT screening strategies and will perform multivariable logistic regression to identify patient, clinician, and site-specific factors that may be associated with uptake of the CDS.

As additional secondary outcomes, for patients who consent to SHS completion, we will perform multivariable logistic regression to identify demographic and behavioral factors associated with GC/CT testing consent and GC/CT positivity.

Specific Aim 2. To determine the most cost-effective approach for GC/CT detection (i.e. usual care, targeted screening, and universally-offered screening) in an adolescent ED population.

Cost-effectiveness analysis: Markov state transition models will be built using readily available software (Decision Maker, Boston, MA). Health states will include those that impact prognosis, cost and quality of life, such as asymptomatic and symptomatic infection with GC and/or CT, pelvic inflammatory disease, infertility, ectopic pregnancy, and chronic pelvic pain. Because the median ED LOS for an adolescent is 4.25 hours, and we have previously demonstrated no significant difference in LOS between patients who completed the SHS compared to those who did not,¹⁷ time to complete survey will not be entered into the model. Furthermore, during a 4-hour ED visit, there is ample time to collect a urine sample, and urine testing is often already requested for clinical care. Therefore, time to obtain samples will also not be included in the cost analysis. We will use a one-month cycle length and a life-long time horizon. Patients will move between health states over time depending upon events that occur in each one-month cycle of the simulation. Health states and events will have associated quality of life and costs. We will perform analyses first using base case estimates for all parameters. We will next perform deterministic sensitivity analyses, examining key parameters one, two, or three at a time, to explore the impact of uncertainty and to address other plausible scenarios, such as populations with lower or higher prevalence of STIs. We also will be able to test various cut points for the STI risk prediction tool, described in aim 2, to see if there is an optimal cut point that minimizes the incremental cost-effectiveness ratio, finding the best balance between sensitivity and specificity for the risk prediction tool. Finally, we will perform probabilistic sensitivity analyses, using second order Monte Carlo modeling, to generate cost-effectiveness acceptability curves, providing further insights into the proportion of the time that the winning strategy will be cost-effective.

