1.1 Hypotheses

The hypotheses of this study are:

- 1a. A higher number of GC/CT infections will be detected during implementation of universally-offered and targeted screening strategies when compared to usual care.
- 1b. The efficiency (cases detected/patients tested) of GC/CT detection will be higher during implementation of a targeted screening strategy when compared to a universally-offered screening strategy.
- 2a. Universally-offered screening will NOT be cost-effective compared with a targeted GC/CT screening approach when applied to the overall population of adolescents treated in emergency departments.
- 2b. Universally-offered screening will be cost-effective compared with targeted screening in adolescent emergency department populations with a high prevalence of GC/CT.

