STI Screening vs STI Testing: There is often confusion as to what constitutes STI testing versus STI screening. Testing typically involves patients who are symptomatic or have a reason for testing, such as a recent known exposure. Alternatively, screening involves an asymptomatic population of patients. Furthermore, STI screening may use a universal approach where all adolescents are offered screening, or a more targeted approach, where only those with identified risk factors are screened.

Electronic surveys using patient reported outcome (PRO) measures may help overcome ED STI screening barriers: There is growing interest in the use of PROs in medicine as we strive to deliver patient-centered healthcare. PROs are defined by the FDA as any report of the status of a patients health condition, health behavior, or experience that comes directly from the patient instead of through another individual (e.g. healthcare provider, parent, etc.) and is not limited to health outcomes. Use of PROs leads to better communication and decision-making between healthcare providers and patients, and improves patient satisfaction and outcomes. The use of PROs to ascertain information about sexual health among adolescents is particularly appealing due to the sensitive nature of the topic. Adolescents cite privacy concerns as a potential barrier to disclosing sensitive health information in the clinical setting. Obtaining sexual health information confidentially in the ED can be challenging due to space/privacy issues, difficulty separating a patient from the caregiver in an acute setting, limited time, competing priorities, and lack of clinical comfort and training. Electronic-based surveys and interventions may obviate some of these barriers. Our previous qualitative work demonstrates that adolescents and caregivers cite improved confidentiality as one of the benefits of using tablet-based technology to offer STI screening in the ED setting. Electronic surveys not only provide a confidential method for obtaining sensitive health information, but they are also efficient and patient friendly, as they can be tailored to an individuals needs through the use of skip patterns and audio assistance. Adolescents do not require a separate room for an interview, and thus, the surveys can be administered while they are awaiting clinical care. This method is also provider friendly and allows for an efficient way to ascertain sensitive health information.

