5.2 Sample Size Calculations and Statistical Power

Workflow Analyses: We estimate that we will observe between 20-30 individuals per site, which is a common sample size for studies of ED workflow processes.

Difference	Power
0.5%	80%
0.75%	98%
1%	99%

Table 2: Power Calculations

Pragmatic Trial: We plan to enroll at 6 PECARN sites. Based on PECARN data, with 6 sites for 52 two-week periods, we conservatively anticipate that approximately 288 patients or more per two weeks per site will arrive. Of these, we conservatively expect to enroll 242 per site. About 220 of these will be asymptomatic and included in the primary analysis. Our preliminary data reveal STI screening rates of 0.16% (usual care) leading to detection rates less than 0.02%. Asymptomatic STI detection rates range from 4-10% in a population of universally offered screening. In a targeted population, which makes up about 1/3 of the overall asymptomatic population, 10-14% will test positive. This leads to estimated detection rates of approximately 3-5%. For power calculations, we assume a detection rate of 4.5% using a targeted strategy and a standard deviation in rates across sites of 2%. Based on expected enrollment of 220 asymptomatic patients per time period per site, we will have approximately 99% power to detect a 1% difference in detection rates, and over 80% power to detect a difference as small as 0.5% between targeted and universally offered strategies (see table above). A 1% difference in detection corresponds to approximately 450 additional STIs detected per year at these sites alone. If results from this study inform screening at centers across the country, the numbers captured could be orders of magnitude higher. Additionally, we will also have adequate power for subgroup analyses based on gender, age, race/ethnicity, and symptomatology, as the design will provide over 90% power to show a difference in detection rates of 2% for subgroups as small as 40 patients per month. Confidence intervals around detection rates in each of the screening strategy groups will be smaller than +/- 0.3%.

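### As worded, the hypothesis 1b efficiency outcome is not limited to asymptomatic patients, so its targeted-minus-universal difference mixes case mix with screening efficiency

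*Combined protocol and SAP*

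**What the plan says.** Section 5.1 defines the primary detection rate as "number of STIs detected divided by the number of eligible, asymptomatic patients". Later in the same paragraph it adds: "We will perform a similar analysis using the outcome of rate of positivity among those tested for GC/CT". That sentence names a new numerator and denominator and does not mention symptoms. It is the only analysis in the plan that serves hypothesis 1b, which section 1.1 words as follows: "The efficiency (cases detected/patients tested) of GC/CT detection will be higher during implementation of a targeted screening strategy".

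Section 2.2 distinguishes testing, typically of patients with symptoms or a known exposure, from screening: "Alternatively, screening involves an asymptomatic population of patients".

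Symptomatic patients are in the study population. Section 3.2 makes patients eligible whatever brought them to the ED. Under section 4.1, a sexually active patient who reports symptoms is classed as high risk in the targeted phase and prompts the strongest testing recommendation. In the universal phase the clinician does not see the survey results. Section 7.4 seeks data on every STI test in patients who meet the inclusion criteria.

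Section 5.2 gives the numbers per site and two-week period: "Of these, we conservatively expect to enroll 242 per site" and "About 220 of these will be asymptomatic and included in the primary analysis". On the targeted strategy it says: "In a targeted population, which makes up about 1/3 of the overall asymptomatic population, 10-14% will test positive".

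**The concern.** Hypothesis 1b asks whether targeting finds more infections per test than offering screening to everyone. If the denominator is everyone tested, it combines screening tests in asymptomatic patients with diagnostic tests in symptomatic ones. The number of symptomatic patients tested may be much the same in both phases, while the targeted phase should produce far fewer screening tests. The same diagnostic tests then weigh more heavily in the targeted rate.

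No difference in how symptomatic patients are managed is needed for this. It is enough that their positivity differs from that of screened patients. The 1b estimate would then be a mixture, and readers could not tell how much of it is screening efficiency.

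**Working it through.** **Inputs from section 5.2 (per site, per two weeks)**
- Enrolled 242, asymptomatic 220, so symptomatic 242 − 220 = 22.
- Target group 1/3 of asymptomatic patients: 220/3 = 73.3.
- Target-group positivity 10-14%. Universal 4-10%; the plan calls this a detection rate, and I treat it as positivity, which is the same thing at full uptake.
- Usual-care screening rate 0.16%.

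**Inputs assumed (not in the documents)**
- Symptomatic positivity q of 15-30%.
- Uptake of asymptomatic testing of 30-80%, equal in both phases.
- 80% of symptomatic patients tested: 0.8 × 22 = 17.6. Section 2.2 is a loose guide only: almost 20% of females with potential STI complaints lacked a documented sexual history or testing.

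**1. The plan's own figure.** Detection rate = share tested × positivity. 1/3 × 10% = 3.3% and 1/3 × 14% = 4.7%, matching the stated approximate 3-5%. The plan gives no expected value or power for positivity among those tested.

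**2. Symptomatic share of tests.** With nA asymptomatic and nS symptomatic tests, w = nS/(nA + nS).
- Everyone tested: targeted 22/(73.3 + 22) = 23.1%; universal 22/(220 + 22) = 9.1%.
- 80% uptake, 17.6 symptomatic tests: 17.6/(58.7 + 17.6) = 23.1%; 17.6/(176 + 17.6) = 9.1%.
- 30% uptake, 17.6 symptomatic tests: 17.6/(22 + 17.6) = 44.4%; 17.6/(66 + 17.6) = 21.1%.

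**3. True screening positivity 12% against 5% (difference 7.0 points).** Observed positivity = (1 − w)p + wq, where p is asymptomatic positivity.

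| Uptake | q | Targeted | Universal | Difference |
|---|---|---|---|---|
| 80% | 15% | 12.7% | 5.9% | 6.8 |
| 80% | 20% | 13.8% | 6.4% | 7.5 |
| 80% | 30% | 16.2% | 7.3% | 8.9 |
| 30% | 15% | 13.3% | 7.1% | 6.2 |
| 30% | 20% | 15.6% | 8.2% | 7.4 |
| 30% | 30% | 20.0% | 10.3% | 9.7 |

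At the midpoints of the plan's two ranges (12% and 7%, true difference 5.0), the 23.1% and 9.1% shares give 5.0, 5.7 and 7.1 points at q = 15, 20 and 30%.

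**4. Where the direction turns.** The distortion is zero when q = (wT·pT − wU·pU)/(wT − wU), with T for targeted and U for universal. For 12% against 5% this is (0.231 × 12 − 0.091 × 5)/0.140, about 17%, at 80% uptake. At 30% uptake it is (0.444 × 12 − 0.211 × 5)/0.234, about 18%. Below that value the gap narrows; above it the gap widens.

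**5. Equal true positivity of 8% in both phases.** The spurious difference is (wT − wU)(q − p).
- 80% uptake: 0.140 × (15 − 8) = 1.0 and 0.140 × (30 − 8) = 3.1 points.
- 30% uptake: 0.234 × 7 = 1.6 and 0.234 × 22 = 5.1 points.

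**6. Unequal uptake: 80% targeted, 40% universal.** Here wU = 17.6/(88 + 17.6) = 16.7%, so wT − wU = 0.064. At equal 8% positivity the spurious difference falls to 0.4, 0.8 and 1.4 points for q = 15, 20 and 30%.

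**7. Usual-care periods.** 220 × 0.0016 = 0.35 asymptomatic tests per site-period, so restricted positivity is undefined in most of them.

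**The case against.** The strongest reply is that the restriction is implied. The positivity outcome follows the primary one in the same paragraph and is introduced as a similar analysis, so the asymptomatic population might carry over. That reading is possible, and a reader should not infer that the plan expressly includes symptomatic tests; no section says so. But no section says the population carries over either. The sentence supplies its own denominator, and symptomatic patients are both eligible and captured. Two analysts could compute different numbers from the same text.

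A second reply is that all-tested positivity is a legitimate estimand. Hypothesis 1b concerns efficiency while a strategy is in use, the trial is pragmatic, and symptoms are among the triggers for the targeted recommendation. This stands as a reason to report that version, but as a separate quantity from screening efficiency.

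A third reply concerns size. Symptomatic positivity appears nowhere in the documents. The one-third figure is a population share, and becomes a ratio of tests only if uptake is equal. Patients in the universal phase may decline whatever their risk, so uptake could differ, and step 6 shows how much smaller the effect can then be. All of this stands.

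**Conclusion.** The 1b outcome as written lacks the restriction used for the primary outcome, and that can change its estimate. Under the stated assumptions, a true 7.0-point advantage is reported as roughly 6.2 to 9.7 points. If symptomatic and screening positivity were equal within each phase, there would be no distortion.

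A reader might infer that the trial could confirm 1b spuriously. The arithmetic permits a gain of about 1 to 5 points when true screening positivity is equal at 8%. But equality means risk targeting selects nothing, and section 5.2 expects 10-14% against 4-10%, ranges that meet only at 10%. Nor is the distortion always in favour of targeted screening: step 4 shows it can go either way.

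False-significance rates should not be quoted as a property of the plan. In simulations of the planned model on an approximate rebuild of the example in Figure 2, with equal 10% positivity and full uptake, rejection ran from 0.5% (11 symptomatic tests per site-period, q = 15%) to 100% (22 tests, q = 30%).

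The primary comparison of detection rates is not affected by this point.

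**What to change.** In section 5.1, define the 1b outcome as asymptomatic patients testing positive divided by asymptomatic patients tested, with the same symptom definition as the primary outcome. State how symptom status is set when there is no survey (baseline periods and patients who decline); the primary outcome needs that rule too. Report positivity among all patients tested as a secondary result, labelled as the strategy as delivered.

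The three-level model cannot be reused unchanged, because usual-care periods contain almost no asymptomatic tests. Fit the restricted outcome to targeted and universal periods only, or analyse individual tests.

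The cost is a few sentences and no data beyond what the primary outcome already requires. The denominator holds fewer tests, so precision is slightly lower.
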